7.3 ASSESSMENT OF ADVERSE EVENTS

Each AE will be assessed by the Investigator with regard to the following categories.

7.3.1 Seriousness

An SAE is defined as any untoward medical occurrence that at any dose is one of the following:

- Results in death
- Is life threatening (an adverse event or suspected adverse reaction is considered “life threatening” if, in the view of either the investigator or sponsor, its occurrence places the patient or subject at immediate risk of death. It does not include an adverse event or suspected adverse reaction that, had it occurred in a more severe form, might have caused death)
- Requires inpatient hospitalization or prolongation of existing hospitalization
- Results in a persistent or significant incapacity or substantial disruption of the ability to conduct normal life functions
- Is a congenital anomaly or birth defect
- Is a medically important event (examples of such medical events include allergic bronchospasm requiring intensive treatment in an emergency room or at home, blood dyscrasias or convulsions that do not result in inpatient hospitalization, or the development of drug dependency or drug abuse)

The FDA has recently defined additional “**Medically Important Events**” that should also be reported as SAEs (Guidance for Industry, Drug-Induced Liver Injury: Premarketing Clinical Evaluation, FDA, July 2009). These include cases where:

- Aminotransferases (ALT or AST) are > 3 times the upper limit of normal (ULN) with an associated elevation of total bilirubin > 2 times ULN without evidence of hemolysis or with alkaline phosphatase < 2 times ULN or not available, or
- ALT or AST activity that is > 5 times ULN

All patients with the above abnormalities should return as soon as possible or within 48 hours to the site for further evaluation of the abnormalities, including repeat ALT and AST measurements; total and direct bilirubin; alkaline phosphatase; and related laboratory assessments of albumin, PT and PTT, creatinine kinase, and GGTP or 5’nucleotidase. Hepatitis A, B, and C, hemolysis, and biliary obstruction should be ruled out. A detailed medical and drug use history should be taken to exclude all potential causes. All such laboratory tests should be performed locally if they are not listed in **Section 4.3.2; Table 1**.

Medical and scientific judgment should be exercised in deciding whether a case is serious and whether expedited reporting is appropriate as in the example above for “**Medically Important Event**.” The medical monitor should be consulted.

7.3.2 Intensity (Severity)

Investigators should assess the severity of AEs according to the following general categorical descriptors:

Mild: Asymptomatic or mild symptoms; clinical or diagnostic observations only; intervention not indicated

Moderate:	Minimal, local, or noninvasive intervention indicated; limiting age appropriate instrumental activities of daily living (ADL) (instrumental ADL includes dressing, grooming, hygiene, home skills, school skills, using the telephone, managing money, etc.)
Severe:	Medically significant but not immediately life-threatening; hospitalization or prolongation of hospitalization indicated; disabling; limiting self-care ADL (self-care ADL includes bathing, dressing and undressing, feeding self, using the toilet, taking medications, and not bedridden)

It is important to distinguish between serious and severe AEs. Severity is a measure of intensity, whereas seriousness is a regulatory definition as per **Section 7.3.1**. An AE of severe intensity may not necessarily be considered serious (by definition) or a mild AE (mild stroke) may be considered an SAE.

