6.3.1 Individual Patient Stopping Criteria

Adverse events due to study drug that affect individual patient safety may necessitate dose interruptions or early discontinuation as described in this section.

Plecanatide therapy in adults with IBS-C and CIC has caused diarrhea in 4% and 5% of patients respectively, with severe diarrhea occurring in 0.7% and 0.6% of patients respectively. Severe diarrhea may cause dehydration. Pediatric patients may be at increased risk for diarrhea and dehydration with plecanatide therapy.

In general, study drug dosing should not be modified for mild diarrhea (Grade 1: increase of < 4 stools per day over baseline) or mild dehydration (Grade 1: dry mucous membranes, diminished skin turgor) (*National Cancer Institute, Common Terminology Criteria for Adverse Events [CTCAE] v5.0, November 27, 2017*). If study drug is not well tolerated by an individual patient, treatment will be permanently discontinued for that patient.

The following guidelines should be used in the case of moderate or severe diarrhea or dehydration:

Table 4 Individual Patient Stopping Criteria

Worst Observed Toxicity Grade NCI Common Toxicity Criteria	Dose Modification for Study Drug
Diarrhea	
Grade 2: Increase of 4-6 stools per day over baseline	No intervention required
Grade 3: Increase of ≥ 7 stools per day over baseline, incontinence, hospitalization indicated	Interrupt study drug for < 7 days until resolved to less than Grade 2 severity. If diarrhea was study drug-related, permanently discontinue study drug. If diarrhea was not study drug-related, e.g., viral gastroenteritis, then consider resuming treatment after consultation with Sponsor's Medical Monitor
Grade 4: Life-threatening consequences, urgent intervention indicated	Permanently discontinue study drug
Dehydration	
Grade 2: IV fluids indicated < 24 hour	Interrupt study drug for < 7 days until resolved to less than Grade 2 severity. If dehydration was study drug-related, permanently discontinue study drug. If dehydration was not study drug-related, consider resuming treatment after consultation with Sponsor's Medical Monitor
Grade 3: IV fluids or hospitalization indicated	Permanently discontinue study drug

Table 4 Individual Patient Stopping Criteria

Grade 4: Life-threatening consequences, urgent intervention indicated	Permanently discontinue study drug
---	------------------------------------

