5.3.1. Adverse Events

Adverse events will be mapped to a Medical Dictionary for Regulatory Activities (MedDRA) version 23.0 preferred term and system organ classification. If a subject experiences multiple events that map to a single preferred term, the greatest severity grade (mild, moderate, or severe), and strongest investigator assessment of relation (reasonable possibility, no reasonable possibility) to study medication will be assigned to the preferred term for the appropriate summaries. Should an event have a missing severity or relationship, it will be classified as having the highest severity and/or strongest relationship to study medication. Overall summary of TEAEs will be provided. The occurrence of treatment-emergent adverse events (TEAEs) will be summarized by treatment group using preferred terms, system organ classifications, and severity. Separate summaries of treatment-emergent serious adverse events (SAEs), TEAEs related to study drug, severe TEAEs, and TEAEs leading to the discontinuation of study will be generated using system organ class and preferred terms. All adverse events reported will be listed for individual subjects showing both verbatim and preferred terms. All adverse events that occurred prior to the initiation of study treatment will be excluded from the tables but will be included in the listings.

Missing onset dates will be imputed as previously outlined in [Section 3.3.5](#) as required to determine treatment-emergent events.

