14.2.6.1.X	Summary of Weekly Stool Consistency (mBSFS-C) by Study Week FAS Population – <Age Group>
14.2.6.2.X	Summary of Weekly Stool Consistency (mBSFS-C) by Study Week PP Population – <Age Group>
14.2.7.1.X	Summary of Rescue Medication Use by Study Week FAS Population – <Age Group>
14.2.7.2.X	Summary of Rescue Medication Use by Study Week PP Population – <Age Group>
14.2.8.1.X	Summary of Weekly Fecal Incontinence Rates by Study Week FAS Population – <Age Group>
14.2.8.2.X	Summary of Weekly Fecal Incontinence Rates by Study Week PP Population – <Age Group>
14.2.9.1.1.X	Summary of Weekly Defecation Pain Rates by Study Week FAS Population – <Age Group>
14.2.9.1.2.X	Summary of Weekly Defecation Pain Rates by Study Week PP Population – <Age Group>
14.2.9.2.1.X	Summary of Weekly Defecation Pain Scores by Study Week FAS Population – <Age Group>
14.2.9.2.2.X	Summary of Weekly Defecation Pain Scores by Study Week PP Population – <Age Group>
14.2.10.1.X	Summary of Weekly Large Diameter Stool Rates by Study Week FAS Population – <Age Group>
14.2.10.2.X	Summary of Weekly Large Diameter Stool Rates by Study Week PP Population – <Age Group>
14.2.11.1	Summary of KINDL® Health-Related Quality of Life by Study Week FAS Population
14.2.11.2.X	Summary of Subject Global IBS-Disease Severity by Study Week FAS Population – <Age Group>
14.2.11.3.X	Summary of Global Relief of IBS Symptoms by Study Week FAS Population – <Age Group>
14.2.11.4.X	Summary of Global Relief of Abdominal Pain by Study Week FAS Population – <Age Group>
14.2.11.5.X	Summary of Global Relief of Treatment Satisfaction by Study Week FAS Population – <Age Group>
14.2.11.6.X	Summary of Global Relief of Treatment Continuation Assessment by Study Week FAS Population – <Age Group>

Safety

14.3.3.1.X	Summary of Treatment-Emergent Adverse Events Safety Population – <Age Group>
14.3.3.2.X	Treatment-Emergent Adverse Events by System Organ Class, Preferred Term, and Greatest Severity Safety Population – <Age Group>

14.3.3.3.X	Treatment-Emergent Serious Adverse Events by System Organ Class and Preferred Term Safety Population – <Age Group>
14.3.3.4.X	Treatment-Emergent Adverse Events Related to Study Drug by System Organ Class and Preferred Term Safety Population – <Age Group>
14.3.3.5.X	Treatment-Emergent Severe Adverse Events by System Organ Class and Preferred Term Safety Population – <Age Group>

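### Protocol 7.3.2 lists dressing under both moderate and severe, so an adverse event graded only on difficulty dressing fits two grades and no rule chooses between them

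*Combined protocol and SAP*

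**What the plan says.** Protocol 7.3.2 sets the scale: "Investigators should assess the severity of AEs according to the following general categorical descriptors". Part of the moderate definition is a limit on age-appropriate instrumental activities of daily living (ADL), explained as "instrumental ADL includes dressing, grooming, hygiene, home skills, school skills, using the telephone, managing money, etc". Part of the severe definition is a limit on self-care ADL, explained as "self-care ADL includes bathing, dressing and undressing, feeding self, using the toilet, taking medications, and not bedridden".

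SAP 5.3.1 has two rules on severity. For several events under one term: "If a subject experiences multiple events that map to a single preferred term, the greatest severity grade (mild, moderate, or severe") is assigned. For a blank grade: "Should an event have a missing severity or relationship, it will be classified as having the highest severity".

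The SAP then reports the grade. Section 9.1 includes a table by greatest severity (14.3.3.2.X) and a separate one, "Treatment-Emergent Severe Adverse Events by System Organ Class and Preferred Term Safety Population" (14.3.3.5.X). Section 9.3 adds a listing of severe or life-threatening events (16.2.7.4).

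**The concern.** The two ADL lists are what separates moderate from severe when an event is graded on its functional effect. They can do that only if no activity is in both, and dressing is in both. Two investigators who each follow the text correctly can give the same event different grades.

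Safety is part of the primary objective, and about 20 sites grade events independently. What is at stake is the consistency of the moderate and severe counts in the safety outputs.

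**Working it through.** No figure in the plan depends on this wording, so the check is a comparison of texts.

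**Step 1. Set the two lists in 7.3.2 side by side.**

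| Activity | Moderate (instrumental) | Severe (self-care) |
|---|---|---|
| Dressing | listed | listed, with undressing |
| Grooming, hygiene | listed | not listed |
| Home skills, school skills, telephone, money | listed | not listed |
| Bathing, feeding, toilet, medications, not bedridden | not listed | listed |

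Dressing is the only activity named in both.

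**Step 2. Apply the definitions to single events.**

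- Limits school skills only: moderate.
- Limits use of the toilet: severe.
- Disabling, or hospitalization indicated: severe, whatever the effect on dressing.
- Limits dressing, with no other severe criterion met: fits both moderate and severe.

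Only the last case is ambiguous.

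**Step 3. Look for a rule that settles it.** Protocol 7.3.2 does not say to take the higher grade when two descriptors fit. The rest of the adverse event text (protocol Section 7 and 8.10, SAP 3.3.7 and 5.3.1) does not either. The SAP's first rule compares grades already recorded for several events under one preferred term. Its second applies only when no grade was recorded. A single event with a recorded grade falls under neither.

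**Step 4. Trace where the grade is used.** Protocol 7.4 requires intensity in every adverse event report, and 8.10 plans summaries by intensity. SAP 5.3.1 asks for summaries by severity and a separate summary of severe events, which become tables 14.3.3.2.X and 14.3.3.5.X. Listing 16.2.7.4 also selects on the grade.

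**Step 5. Trace where it is not used.** The individual stopping criteria in Table 4 (protocol 6.3.1) are headed "Worst Observed Toxicity Grade NCI Common Toxicity Criteria", and the study-level criteria in 6.3.2 are also written in toxicity grades. SAP 5.3.2 grades laboratory toxicities by CTCAE. Seriousness has its own definition in protocol 7.3.1. No efficacy endpoint uses adverse event severity.

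**The case against.** The strongest reply is that this is one duplicated word in descriptors the protocol itself calls general, so investigator judgment is expected. The adverse events that protocol 2.3 expects are diarrhea, cramps, gas and bloating, and 7.1 generally keeps abdominal pain, abdominal discomfort and defecation pain out of the adverse event database. The limits most plausible for the expected events are toilet use, listed only under severe, and school skills, listed only under moderate. Grading is done under the blind, so ambiguity should mainly add noise rather than favor an arm. Adverse events are summarized descriptively; hypothesis tests are planned only for efficacy.

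All of this limits the reach of the point and stands. It does not remove the contradiction. Judgment can apply two categories but cannot separate them when both name the same activity.

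A reader might infer more than the documents support, in three ways:

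- **That the severe-event table as a whole is unreliable.** Every other severe criterion decides the grade without reference to dressing.
- **That hygiene (moderate) and bathing (severe) are a second duplication.** The lists use different words, so this overlap is an inference.
- **That the effect can be sized from the denominators.** One event is 1/30 = 3.3 percentage points in an arm of 30. It is 1/150 = 0.67 points across the five active arms (5 × 30 = 150). The adult IBS-C difference in severe diarrhea in protocol 2.1.5 is 1.0% − 0.1% = 0.9 points. But the first two figures are the weight of any single event and do not say how many would be ambiguous. Nothing suggests that a diarrhea grade would turn on dressing. The benchmark is also unsettled: 6.3.1 gives 0.7% for severe diarrhea in adult IBS-C, which against the same 0.1% makes 0.6 points.

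**Conclusion.** The point holds in a narrow form. An adverse event whose only deciding functional effect is difficulty dressing meets both the moderate and the severe definition in protocol 7.3.2, and neither document says which applies. This is a contradiction in a working grading rule, because the recorded grade goes directly into two planned tables and one listing.

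The number of affected events cannot be estimated from the documents and may be small or zero. The conclusion assumes only that investigators grade from the text of 7.3.2 and that no instruction outside these documents settles the overlap.

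**What to change.** Either of two changes to protocol 7.3.2 is enough:

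- Name dressing under one level only. Grooming and hygiene should stay assigned to a level: they appear only in the moderate list, so deleting them there would leave them under none.
- Or add one sentence saying that an event meeting both descriptors takes the higher grade. This matches the direction of the SAP's existing conventions for multiple events and missing grades.

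The change should reach all sites at the same time.

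The wording itself costs almost nothing. SAP Section 7 (Version 2.0) describes COVID-19 handling for subjects in the study, so some events may already have been graded. In that case, check the events graded on the ADL criterion, with site queries where dressing decided the grade. The blinded data review meeting in SAP 3.4 is planned for deciding population membership before unblinding, and the check can be added to it. That limited re-check is the only real cost. No new data collection or analysis is needed.

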7.3.3 Causality

The investigator will assess the causality/relationship between the study drug, or study procedure, and the AE and record that assessment in the eCRF.

The causal relationship of the AE to study drug will be described in terms of:

Reasonable Possibility:	There is evidence to suggest a causal relationship between the drug and the AE (e.g., the AE is uncommon and known to be strongly associated with drug exposure or is uncommon in the study population but not commonly associated with drug exposure)
No Reasonable Possibility:	There is no evidence to suggest a causal relationship between the drug and the AE

The study conduct relatedness for AEs and SAEs will also be assessed and documented. The most likely cause of an AE or SAE (e.g., disease under treatment, concomitant disease, concomitant medication, other) will be indicated in the eCRF system with details of the concomitant disease or medication or other cause.

7.4 RECORDING ADVERSE EVENTS

Adverse event assessment and reporting will extend from signing of ICF until completion of the final visit (End of the Post-Treatment Period). Adverse events occurring from the time of ICF signing up to the intake of the first dose of study medication will be classified as pre-existing conditions for this study and therefore will be recorded in the Medical History page of the eCRF. If, however, an event is considered a serious adverse event (as defined below) and occurs after the signing of informed consent but before randomization (i.e., during screening), this will be collected and reported as non-treatment-emergent Serious Adverse Events and will be recorded in the Adverse Event page of the eCRF. Events that occur from time of first dose of study drug until completion of the final study visit will be considered Treatment-Emergent Adverse Events and will be recorded on the AE page of the eCRF. Adverse events occurring after the end of the study should be reported to the Sponsor by the Investigator only if the event meets at least one seriousness criterion and the Investigator considers the causal relationship to the study drug as 'reasonably possible'.

All AE reports should contain a brief description of the event, date of onset, date of resolution, intensity, treatment required, relationship to study drug, action taken with the study drug, outcome, and whether the event is classified as serious.

All AEs experienced by patients who are randomized to treatment, regardless of the relationship to study drug, will be recorded in the eCRF. For patients who are screen failures, only SAEs (if any) will be reported on the AE page of the eCRF.

**See Section 7.6 on requirements and expectations for follow up of Adverse Events.*

7.5 REPORTING SERIOUS ADVERSE EVENTS

[figure not shown]
All SAEs that occur during the study, as defined by the protocol, must be reported by the Investigator to the designated SAE Safety Contact by submitting (faxing or emailing) the SAE Form **within 24 hours** from the point in time when the Investigator becomes aware of the SAE. In addition, all SAEs including any deaths, which occur up to and including 30 days after the administration of the last dose of the study medication, must be reported to the designated Safety Contact **within 24 hours**.

All SAEs will be collected and reported from signing of informed consent/assent until the end of the study. All SAEs that occur from signing of the ICF/assent to 30 days after the last dose of study medication must be reported whether or not considered causally related to the study medication. Any SAE that occurs beyond 30 days after last dose of study medication must be reported to the designated safety contact only if the event is considered (in the opinion of the Investigator) causally related to the study drug.

SAE forms will be provided to each clinical site. The information collected will include a minimum of the following: protocol number, Investigator information, patient number, event term, a narrative description of the event including its start date, and an assessment by the Investigator as to the intensity and possible relatedness to study medication. A sample of the SAE form can be found in the study manual. The Medical Monitor or Synergy may request follow up information regarding the SAE.

The Investigator will prepare or directly oversee preparation of each SAE report and the Medical Monitor will evaluate and confirm the seriousness and the causal relationship of the event to study treatment. In addition, the Investigator and Medical Monitor will evaluate the expectedness according to the reference document (Investigator's Brochure). Based on the Medical Monitor's and Sponsor's assessment of the event, a decision will be made concerning the need for further action.

The initial SAE Report Form must be faxed or emailed by the Investigator to the designated Safety Contact (below) within 24 hours of becoming aware of the event:

For any questions related to the reporting of an SAE, sites should call the Safety Contact and include the following information: Sponsor (██████████), protocol number (SP304202-14), and contact information.

The minimum information required for an initial report is:

- Name of person sending the report (i.e., name and address of Investigator)
- Patient identification (site number, patient number, initials, NOT patient name)
- Protocol number
- Description of SAE
- Causality assessment, if possible

However, as far as possible all points on the SAE form should be covered in the initial report, or the completed SAE form itself must be faxed to the designated Safety Contact. In addition, the event must be documented in the eCRF.

After receipt of the initial report, the Safety Contact and safety center will review the information and, if necessary, contact the Investigator, to obtain further information for assessment of the event. Acknowledgement of receipt of the SAE report will be sent to the site within 24 hrs. In the event acknowledgement is not received, the site should contact Research Assist Inc.

All SAEs must be reported by the Investigator to their IRB/IEC in writing, as well as appropriate regulatory authorities, as required by law. The designated Synergy Safety Contact will be responsible for all information processing and reporting according to local legal requirements.

7.6 FOLLOW-UP OF ADVERSE EVENTS

All AEs experienced by a patient, irrespective of the suspected causality, will be monitored until the AE (including abnormal laboratory values) has resolved or has returned to baseline or stabilized at a level acceptable to the investigator and medical monitor; until there is a satisfactory explanation for the changes observed; until the patient is lost to follow-up; or until the patient has died. **The recording of a stop or stabilized date is required for all reported adverse events.** The handling of a missing AE stop date when a patient is lost to follow-up or when an adverse event is considered stable but ongoing at the end of study visit will be outlined prior to database lock.

